3. POTENTIAL BENEFITS OF THE PROPOSED RESEARCH TO THE SUBJECTS AND OTHERS

The potential benefits of the proposed research involve learning about ways to effectively engage men in diabetes prevention programs. The NDPP has been shown to promote weight loss and reduce risk of diabetes. As all participants will have access to the core content of the NDPP, across both arms of the trial, all participants may benefit from accessing it. However, it is possible that participants will not experience weight-loss through participation and may not derive direct benefit for themselves. Nevertheless, accomplishing our Aims, as outlined below will generate knowledge that may promote the wide dissemination of our approach, if effective, potentially benefiting healthcare systems, the population of racial and ethnic minority men at risk for diabetes, and contributing to a reduction in gender and racial/ethnic health disparities.

Aim 1. Assess the effect of Power-Up vs. NDPP on weight loss among racial/ethnic minority men at risk for diabetes. Hypothesis 1 (Primary Outcome): Men randomized to Power-Up will achieve significantly greater weight loss at 16-weeks and 1-year than men in the standard care group referred to mixed-gender NDPP classes.

Aim 2. Compare engagement of racial/ethnic minority men at risk for diabetes in Power-Up vs. NDPP.

Hypothesis 2 (Secondary Outcome): Men randomized to Power-Up will have significantly greater engagement rates (i.e., attend at least 4 sessions) and retention rates (i.e., attend 9 or more sessions) than men randomized to standard care and referred to mixed-gender NDPP classes.

Aim 3. Evaluate the Reach, Effectiveness, Adoption, Implementation, and Costs of Power-Up. (Exploratory Outcomes) Use the RE-AIM framework to evaluate: 1) the reach of our recruitment methods and the representativeness of men who enroll in the study, are successfully engaged, and who are successfully retained in Power-Up vs. standard NDPP, relative to the eligible population; 2) the broader effectiveness of Power-Up based on patient-reported outcomes [e.g., self-reported health, health behaviors, psychosocial

factors] and routinely measured clinical data [e.g., change in blood pressure, change in HbA1c]; 3) adoption of *Power-Up* at the practice level; and 4) the fidelity and consistency of implementation and total program costs of *Power-Up*.

4. IMPORTANCE OF THE KNOWLEDGE TO BE GAINED

Results from this study will 1) increase knowledge about how to engage and retain men in health promotion programming, 2) inform the development of future interventions to prevent diabetes among men, 3) provide much-needed data regarding the incremental effect of a targeted prevention program for men, 4) help inform public health policy regarding the costs and benefits of alternative interventions to reduce the incidence of diabetes. The risk-benefit ratio in the proposed study is acceptable for the following reasons. First, all enrolled individuals will be at high risk for diabetes and will participate in an evidence-based intervention, with proven effectiveness. Second, all participants in the *Power-Up* model will receive a tailored program that has shown to be acceptable to men and may improve engagement and weight loss outcomes.

Contact PD/PI: [name]

Data and Safety Monitoring Plan

This study is a Phase III Clinical Trial of a behavioral intervention being tested in a translational, randomized controlled trial for with prediabetes. Information on the study will be provided to participants by telephone, in writing via mail, and in person. The intervention does not convey more than minimal risk, and there is no reason to suspect that any serious adverse events will be attributable to it. The most serious risk connected with the study is a potential breach of confidentiality. The Data and Safety Monitoring Plan will address risk and will outline procedures for reporting adverse events that may be expected from participants ≥ 18 years old with prediabetes, even though no such events are expected to be attributable to the intervention. [name] will assume the responsibilities for data and safety monitoring for this study. All co-investigators and staff will cooperate with [name] to provide all necessary data for this task in the event of any adverse events. Drs. [name] and [name], as co-PIs, are fully responsible for the system remaining intact. [name] will periodically (at least bi-annually) assess and review data collection and storage procedures at both sites to ensure that confidentiality is being maintained.

Adverse Event Monitoring. Participants who miss sessions will be contacted by their coach. If the coach is informed that the participant is hospitalized or deceased, the coach will report that information to AECOM or PCIP/NYC-DOHMH project manager immediately, who will in-turn report it to [name]. The two follow-up surveys (after completion of 16 Core sessions, and after completion of 6 maintenance sessions) also include questions about hospitalizations and other serious adverse events. These surveys will be administered primarily by telephone by our research staff based at our two sites and occasionally in person, when meeting participants to collect missing weights who have also been non-responsive to attempts to schedule a telephone survey, using equivalent procedures to those used for telephone administration. If, 1) the interviewer is informed of an adverse event in the course of the survey, or 2) while trying to reach the participant, the interviewer is informed by someone in the household of a subject's hospitalization or death, that event will be noted. Any hospital admission for a related condition or death from any cause will be immediately reported to [name] who will record them. The Einstein IRB will maintain reports of adverse events.

Information about adverse events will be sought as described above. Unanticipated (non-serious) adverse events will be reported to the IRB within 30 days of such an event using the AECOM IRB Adverse Event Report. Serious adverse events will be reported to the IRB within 48 hours by phone and email. A completed AECOM IRB Adverse Event Report will be submitted within 10 days of initial IRB notification. All deaths will be reported to the IRB within 48 hours of ascertainment. The monitor will maintain a file of all ascertained adverse events that can be used to submit summary reports.

Recruitment Monitoring. Once initial recruitment begins, the study director will compile a weekly and cumulative tally using study identification numbers of recruited and randomized subjects. Drs. [name] and [name] and co-Is will assess on a bi-yearly basis the feasibility of reaching projected recruitment targets based on interim recruitment and retention reports. Regarding retention, all recruited participants will be included in the analyses on an intention-to-treat basis unless they request to be dropped from the study specifically. Participants 1) requesting only an end to the intervention, 2) who cannot be contacted or 3) for whom outcome measures are not available, will be included in the analysis for outcome measures that are available. These latter subjects will not be considered drop-outs for purposes of retention statistics.

Data Safety and Monitoring Board. [name] will have primary responsibility for ongoing monitoring of data related to safety for this study on an on-site, day-to-day basis. He will consult regularly with [name] on the results of his monitoring to discuss any concerns related to safety or the integrity of the study. However, because this is a Phase III Clinical Trial, we will also establish an independent Data Safety and Monitoring Board (DSMB) to oversee the activities of our research trial in order to ensure the safety of participants, the validity of our findings, and the need for further data collection. We propose a DSMB membership that may include a statistician, an expert in diabetes prevention program research, and a

healthcare provider with experience and expertise in the care of prediabetes and diabetes. All of these individuals will also have experience and expertise in the conduct of Phase III Clinical Trials Human Subjects Research. The PIs and investigators will interact with the DSMB at the DSMB's discretion, providing them with material to facilitate fulfillment of the functions detailed below. These include:

Data and Safety Monitoring Plan

Contact PD/PI: [name]

1. Review of protocols, informed consent procedures, and safety plans.
2. Monitor the progress of the intervention, i.e. participant recruitment and retention, risk/benefit ratio for participants, adherence to timetable, and quality of data.
3. Evaluation of the impact of new treatment developments on the risk/benefit ratio of our study.
4. Make recommendations to the PIs about continuation, modification, or termination of the intervention based on adverse events or beneficial outcomes.
5. Request interim analyses.
6. Monitor the confidentiality of the intervention data and the results of monitoring.
7. Offer consultation to the investigators on procedures likely to increase participants' burden, to raise ethical concerns, or to give the appearance of conflict of interest.

The following data will be available to the DSMB Board:

1. All adverse events: We are required to report in writing adverse events to our IRB within 48 days from the time that we become aware of an adverse event. The adverse event forms will be made available to the DSMB as well as tables summarizing the occurrence of specific events; such tables can help identify the systematic occurrence of an adverse event and lead to protective measures. As we are already required to report each event to our IRB, we plan to report to DSMB these adverse events and updated summary tables within 48 hours from each adverse event.

2. Any analyses requested by the DSMB Board.

3. Manuscripts and publications.

The DSMB will convene at least once annually, and more often as needed, either in person if logistically feasible, or by phone/Zoom video conference. The meeting will begin with a progress report by the PIs, followed by a report on any adverse events from [name]. We will then discuss interim results on Reach (characteristics of those who participate vs. refuse), Representativeness; Adoption (percent of practices approached who agree to participate), and Implementation (consistency of study recruitment and assessment procedures, fidelity checklist ratings from coaches and fidelity ratings based on observation by Drs.

[name] and [name], any modifications to the protocol for implementation, etc). To preserve investigator blinding of outcomes that may bias their interpretation of data or approach to the protocol, interim data on Effectiveness will not be reviewed by the investigators or the DSMB, unless specifically requested by the DSMB due to safety concerns. The DSMB will conclude the meeting without the investigators present and will make a recommendation about continuation of the study.

Early Termination. [name] and [name] will determine if the study is to be terminated prior to the scheduled study conclusion, in consultation with our DSMB. Early study termination will be considered in the event of a pattern of unanticipated serious adverse events determined to be possibly, probably or definitely related to the intervention or the data collection. In such a case, interim assessment would also be considered to ascertain if the events were associated with the intervention. In the absence of a pattern of unanticipated serious adverse events, given the minimal risk character of the intervention of this study, traditional statistical stopping rules for efficacy or safety of the intervention would not be applicable. However, early study termination will be considered if:

- subject recruitment falls below 20% of the projected number of subjects 6 months after the initiation of all stepped and potential recruitment strategies have been utilized, or
- if we fail to retain (as defined above) at least 70% of enrolled study subjects at any annual review.

[name] will consult with [name], come to agreement, seek consultation from the DSMB, and report a decision to terminate the study early to the IRBs within 48 hours of the determination and a narrative description of the reasons for early termination within 10 days.

Contact PD/PI: [name]

Overall Structure of the Study Team

The study team will be led by Drs. [name] and [name] (PIs), who are both based at Albert Einstein College of Medicine. Our AECOM study offices will house a project manager and two study coordinators who will have primary responsibility for conducting and overseeing all research activities related to participants recruitment and workshop. Drs. [name] and [name] (Co-Is) are also based at AECOM.

At PCIP/DOHMH [name] will oversee activities related to practice engagement, participant recruitment, assessment, and intervention delivery to participants recruited from PCIP-affiliated primary care practices. She will be supported by a full time onsite research assistant in our PCIP-based study office. She will coordinate regularly with the Einstein-based project manager and receive regular supervision from [name] to ensure consistency of procedures. Together, this team will provide input to the study plans and procedures from both Einstein and PCIP/DOHMH.

All *Power-Up* coaches will be hired by the Einstein site. These coaches will be dedicated to deliver *Power-Up* PCIP-affiliated practices throughout New York City. The Einstein-based research staff will also coordinate their efforts with the research staff based at PCIP and provide support as needed.

All supplies and materials will be purchased by the Einstein site and delivered as needed to PCIP. All administration of PCIP-related expenses, outside of personnel costs for study staff, will also be carried out by our Einstein staff to maximize efficiency.

[name] will develop procedures for randomization of participants that via an electronic database that can be accessed by both sites and will develop a similar set of procedures and remotely accessible databases for data entry at each of the sites. All transmissions will be encrypted and delivered via secure servers.

[name] (PI) oversees a research lab at the Ferkauf Graduate School of Psychology, Yeshiva University, which is co-located with Einstein. Graduate students in the Clinical Health Psychology PhD program, as well as two post-doctoral fellows under his supervision, have relevant expertise and experience with qualitative interviewing, participant assessment, and data management/analysis. They will be involved in the activities of the proposed study, at PCIP, on an as-needed basis as part of their mentored research experience and training. All trainees who take part in the study will be trained in human subjects research and approved by the Einstein IRB prior to their involvement.

The organizational structure for the proposed project is based on a similar model that has proven effective for the *NYC Care Calls Study*, which enrolled 812 adults with type 2 diabetes from PCIP-affiliated practices. [name] (PI), Drs. [name] and [name] (Co-I) have a history of successful collaboration with [name] and PCIP on this project and this experience will ensure continued success in the proposed collaborative research.

The Dissemination Plan

As recipients of this award, Drs. [name] and [name] will ensure the clinical trial it will support is registered and results are submitted to ClinicalTrials.gov according to the timelines and requirements specified in the NIH Policy on the Dissemination of NIH-Funded Clinical Trial Information (NOT-OD- 16-149). We plan to register once the protocol is finalized during the first 6 months of the award, before any participants are enrolled. However, we will ensure that registration will occur no later than 21 days following enrollment of the first subject to adhere to the expectations for NIH-funded clinical trial information. Updates will be made within the required timeframes, no less than once every 12 months, to reflect any material change in the study status and to keep the record current. Results summary and required documents will be submitted within the timeframes specified in the regulation.

Drs. [name] and [name] will ensure the Informed Consent Forms for all clinical trials under this award include the following FDA specified disclosure statement, exactly as written, notifying subjects that the study will be submitted to ClinicalTrials.gov: *A description of this clinical trial will be available on <http://www.ClinicalTrials.gov>, as required by U.S. Law. This Web site will not include information that can identify you. At most, the Web site will include a summary of the results. You can search this Web site at any time.*

Albert Einstein, has a written internal policy requiring registration and results reporting on ClinicalTrials.gov, in compliance with NIH and FDA requirements. In addition, the internal policy requires timely updates to the study record as required by FDA regulations and NIH policy. To ensure compliance with NIH's registration deadline, the Institutional Review Board (IRB) requires the registration NCT# before the study protocol can receive IRB approval. To enable compliance with all ClinicalTrials.gov reporting requirements, Albert Einstein sends notifications on activities required to keep the study record current and provides personnel, training, and any additional resources needed.

Beyond adhering to these requirements related to ClinicalTrials.gov, we will disseminate our results more broadly, through presentations at national professional and scientific conferences, and in peer-reviewed journal publications, with open access publishing whenever possible. We will also make information about these publications available on our website for the New York Regional Center for Diabetes Translation Research (www.newyorkregionalcdtr.org), one of 8 Centers funded by NIDDK to promote translational research for diabetes prevention and control. We will also disseminate announcements for the publications among the members of our NY-CDTR, working in diabetes prevention and control in the NY-region. We will also reach investigators across the country focused on Latino populations, through our Latino Network for Diabetes Translation Research, a National Resource Core of the NY-CDTR. In total our membership list will reach 90+ investigators across the country. NIDDK also provides a mechanism to share preliminary findings and resulting publications with the other 7 funded CDTRs through a CDTR Directors monthly telephone meeting and a yearly in person meeting that features an e-book highlighting each CDTR's most important publications. Thus, our dissemination will penetrate into the memberships of CDTRs across the country focused on diabetes translation research. The intervention protocol will be made available on the NY-CDTR website and will be submitted to the CDC for distribution as a recognized program.

Our partnership with [name] at the Primary Care Information Project/NYC-Department of Health and Mental Hygiene provides an avenue of local dissemination. Our partner is committed to support the adoption and maintenance of *Power-Up* as a men-focused diabetes prevention program if it is proven to be effective and if costs are demonstrated to be reasonable and in a favorable balance with program benefits by the current study. Through this healthcare system, *Power-Up* could be disseminated to thousands of men obtaining care in diverse healthcare system settings across New York City.

sIRB Communication Plan

The Einstein IRB (Einstein) will be serving as the Single IRB (sIRB) in this proposed multi-site study involving human subjects' research. As the sIRB, Einstein will fulfill the requirements set out in 45 CFR Part 46, and 21 CFR Parts 50, 56, 312, 600, 812, as applicable, by conducting initial and continuing reviews of protocols for all participating domestic sites, including amendments, unanticipated problems, protocol deviations, and required reporting to federal oversight agencies. The sIRB will also serve as the Privacy Board, as applicable, to fulfill the requirements of the HIPAA Privacy Rule for use or disclosure of protected health information for research purposes.

The participating sites identified in the Project/Performance Site Locations section of this proposal have indicated their willingness to rely on Einstein as the selected sIRB and the PIs have obtained documentation of their agreement via letter. In turn, the Einstein IRB has provided a Letter of Support indicating its commitment to serve as the sIRB.

At the time of award, Einstein sIRB representatives will meet with the PIs and Research Study Team to review their responsibilities, as outlined in the relevant Reliance/Authorization Agreements (AA), and to review Einstein's sIRB Policies. It may be determined during this meeting that the use of the Streamlined, Multisite, Accelerated Resources for Trials (SMART) IRB Reliance platform, funded by the National Center for Advancing Translational Sciences (NCATS), is the most efficient model for implementing the authorization agreements among the participating sites.

Prior to the signing of AAs between Einstein and the participating sites, the sIRB will work with the PI and Research Study Team to ensure that the AA is signed by both institutions. The PIs will communicate the terms of the agreements with each participating site. AAs will be considered fully executed once signed by the Institutional Officials at both Lead and Relying Sites.

As outlined in the AAs, the relying institutions will be expected to contact the Lead PI when there are study events, required reports, and other significant issues that must be reported to the sIRB. The Lead PI will communicate with the sIRB for guidance. The sIRB will offer, as needed, to communicate directly with the relying sites to resolve issues.

The PIs will obtain prior approval from NIH to request additional sites to the study. If approved, the PIs will coordinate with the participating site to obtain a signed AA. The same processes as described above will apply.

The Einstein IRB Office will maintain the signed Authorization Agreements and will provide copies to the relying sites.

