physical activity. The NDPP guidelines recommend increasing physical activity at a moderate level, such as brisk walking, but participants will choose their own activity outside of the Core and post-Core learning sessions.

Expression of intent to harm self and/or others. The study will not assess intent to harm self or others, however, though this is a low risk, subjects may express thoughts of harm to self and/or others while completing study questionnaires, especially as it relates to managing their pre-diabetes. Staff and coaches will be trained on how to appropriately respond to expression of intent to harm self or others, and will maintain a Manual of Procedures (MOP), which includes state law requirements and local emergency phone numbers. Healthcare providers can also be alerted about concerns regarding risk, with the participant's consent.

Other Risks. Taking part in this research study may involve providing information that participants consider confidential or private, including thoughts of harm to self and/or others. Coaches and study staff will be trained in emergency procedures for adverse health events that may occur by chance when they are interacting with participants. They will not provide any intervention themselves but will be trained to identify emergency situations (e.g., cardiac arrest) and in procedures to access emergency care (e.g., calling 911). In addition, there is a slight risk of a breach of confidentiality. Subject will be informed of confidentiality limitations in the informed consent. As described in detail below, every effort will be made to keep participant names and contact information secure; only research staff will have access to linked contact information and study data. Identifiers will be excluded from any participant data analyzed by the AECOM-based data analysts.

Alternative Treatments and Procedures. The alternative is for potential subject to not participate in the study. If potential participants decline to enroll in the study but express interest in accessing NDPP, we will inform them of the procedures to do so. All potential participants will be receiving care from sites that provide access to the NDPP.

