Provisions for ensuring necessary medical or professional intervention in the event of adverse effects will be coordinated through [name], but will follow usual PCIP procedures. Adverse events reported directly by lifestyle coaches will be referred directly to [name]. He will also monitor the de-identified data collected on an ongoing basis to ensure the safety of subjects enrolled in our study. We feel that these measures are adequate to protect against risk.

Expression of intent to harm self and/or others. Subject will be informed during consenting about the limits to confidentiality if intent to harm self and/or others is expressed. Study staff shall assess a subject's expression of harming self and/or others. Harm deemed imminent shall be immediately reported to the local authorities as required by state law. Staff will note alert in chart and notify the subject's primary care provider. Intent to harm self and/or others shall be recorded as a Serious Adverse Event at the local and coordinating center IRB. Because surveys will primarily be conducted by phone, we will use the PHQ-8 scale to assess depressive symptoms (See Table 1, Research Strategy), rather than the PHQ-9, to avoid directly inquiring about suicidal risk. Given the target population, true imminent suicidal risk is expected to be exceedingly rare and asking questions about suicidal ideation would mostly yield false positives. However, all staff will be trained in suicidal risk assessment by [name], a licensed clinical psychologist in NY State, and will be trained in a protocol of how to respond to risk with referrals for mental health care at one end of the spectrum of risk and calling 911 and/or crisis response teams at the other.

Breach of confidentiality. Study participants face risks related to inadvertent release of confidential information.

This will be minimized through careful adherence to best practices for data collection and management. All research staff will be trained in principles and methods for assuring participant confidentiality and safety. Efforts, such as keeping research records secure and allowing only authorized people to have access to research records, will be made to keep the information safe. Participants will be given any new information we become aware of that would affect their willingness to continue to participate in the study.

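### The DSMB is promised all adverse events, but the only event questions the protocol describes concern hospitalisations and other serious events, so non-serious events are captured only passively and incompletely

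*Protocol*

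**What the plan says.** **What is promised.** In the Data and Safety Monitoring Plan, the part on the Data Safety and Monitoring Board lists all adverse events first among the data the board will receive. It promises event forms and summary tables, and says of the tables that "such tables can help identify the systematic occurrence of an adverse event and lead to protective measures". Adverse events are also one of the grounds on which the board may recommend continuing, modifying or ending the intervention. Under Adverse Event Monitoring, unanticipated non-serious events go to the IRB within 30 days, and the monitor keeps a file of all ascertained events.

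**How events are found.** Adverse Event Monitoring describes these routes:

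- Coaches: "Participants who miss sessions will be contacted by their coach". Then, "If the coach is informed that the participant is hospitalized or deceased, the coach will report that information" to a project manager.
- Surveys: the two follow-up surveys "also include questions about hospitalizations and other serious adverse events".
- An adverse event that comes up during a survey is noted, with no limit to serious events. So is a hospitalisation or death that someone in the household mentions.

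The section then states: "Information about adverse events will be sought as described above".

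**Elsewhere.** Section 2b, Protection Against Risk, has a wider coach route: "Adverse events reported directly by lifestyle coaches will be referred directly to" the named safety lead, with no restriction to hospitalisation or death. Section 1b says "The NDPP guidelines recommend increasing physical activity at a moderate level", and men are encouraged to ask their provider about safe exercise.

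**The concern.** The reporting promise covers events of every grade. The questions described cover only serious ones. A non-serious event reaches the file when someone happens to mention it, and the plan describes no step that asks.

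The programme encourages men to become more active, so strains, falls and exercise symptoms are foreseeable. The protocol does not name them as expected harms, and it expects no event to be attributable to the intervention. That expectation is what a table of non-serious events could test, but a table built on volunteered reports is a weak test. A near-empty table could mean few events or few mentions, and the board could not tell which. It would have little basis for the use the protocol gives the tables, which is to spot systematic occurrence.

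A later analysis plan cannot repair this, because it cannot tabulate events that were never collected.

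**Working it through.** The protocol states no adverse event rate, so there is no figure to reproduce. The main check is to compare the scope of the routes with the scope of the promise.

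| Route (protocol section) | Who starts it | Serious events | Non-serious events |
|---|---|---|---|
| Survey questions (Adverse Event Monitoring) | Staff ask | Asked | No question described |
| Mention during a survey (same section) | Participant | Noted | Noted if mentioned |
| Word from the household (same section) | Household member | Hospitalisation or death noted | Not covered |
| Coach follow-up of missed sessions (same section) | Coach calls | Hospitalisation or death passed on | Not mentioned |
| Coach-reported events (section 2b) | Coach | Referred | Referred if the coach learns of them and reports them |
| Data for the DSMB | – | All promised | All promised |

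1. In the non-serious column, no route consists of a described question. Two routes are open, and both are passive.
2. By pointing back to these routes, the protocol adds no other source.
3. The coach's scope is stated in two ways: hospitalisation or death under Adverse Event Monitoring, and adverse events without limit in section 2b.

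**Illustration only.** The protocol plans 300 men randomised 1:1, so 300 / 2 = 150 per arm. Two inputs are assumptions: the share of men with an activity-related injury over the year (*i*) and the share of those injuries that is volunteered (*c*). The expected number recorded per arm is 150 × *i* × *c*. The chance that at most one is recorded in an arm, with *p* = *i* × *c*, is (1 − *p*)^150 + 150 × *p* × (1 − *p*)^149.

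| *i* | *c* | *p* | Occurring per arm (150 × *i*) | Recorded per arm (150 × *p*) | Chance of at most one recorded |
|---|---|---|---|---|---|
| 5% | 10% | 0.5% | 7.5 | 0.75 | 83% |
| 5% | 20% | 1% | 7.5 | 1.5 | 56% |
| 5% | 50% | 2.5% | 7.5 | 3.75 | 11% |
| 5% | 80% | 4% | 7.5 | 6 | 1.6% |
| 10% | 10% | 1% | 15 | 1.5 | 56% |
| 10% | 20% | 2% | 15 | 3 | 20% |
| 10% | 50% | 5% | 15 | 7.5 | 0.4% |
| 10% | 80% | 8% | 15 | 12 | below 0.01% |

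The result depends almost wholly on *c*, which nobody will know. The same 1.5 recorded events arise from 7.5 true events at 20% volunteering and from 15 at 10%. The table of recorded events cannot separate the two.

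**The case against.** The strongest reply is that the protocol promises to report what it learns and does not undertake to find every minor event. The monitor's file covers ascertained events, the reporting clock starts when staff become aware of an event, and the 30-day IRB route is limited to unanticipated non-serious events. The trial is classed as minimal risk, safety is not a study outcome, both arms receive the core programme content, and no comparison of adverse events by arm is promised. This stands in part. No IRB duty is broken, and the low risk calls for a light remedy. But the purpose given for the DSMB tables needs more than chance mentions.

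Three stronger readings are tempting, and the document does not support them:

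- *Non-serious events go unseen.* Interviewers note any adverse event mentioned, and section 2b refers coach-reported events without a seriousness limit. Capture is incomplete but not absent. Nor do coaches pass on only hospitalisation or death; that is the wording of one section, and section 2b is wider.
- *The surveys ask only about serious events.* The text says that they include such questions. The instrument is not shown, so one can say only that no other event question is described.
- *Capture follows attendance and so differs by arm.* Hypothesis 2 does expect attendance to differ. But research staff run the surveys as part of follow-up, whether or not a man attends, and coaches call men who miss sessions. Neither the presence nor the direction of such a bias is established.

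It is also fair to say that the illustrative figures restate their assumptions. At 50% volunteering and 10% incidence, an almost empty table would be very unlikely.

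**Conclusion.** The point holds as a mismatch between promise and method. The DSMB is to receive all adverse events in tables meant to reveal systematic occurrence, but the only event questions described concern hospitalisations and other serious events. Followed as written, the protocol captures non-serious events passively. The tables will be incomplete to an unknown degree and cannot be read as a count of all events.

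The size cannot be derived from the protocol. Under the assumed inputs, the number recorded per arm runs from 0.75 to 12 while 7.5 to 15 occur; this illustrates the ambiguity and does not estimate it. The conclusion rests on the survey content as the protocol describes it. If the instrument already asks about non-serious events, what remains is to say so and to align the two statements on coaches. Ascertainment of serious events and the primary weight analysis are not affected. The change is worth making because it is cheap.

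**What to change.** 1. Add one short question to the 16-week and 12-month surveys, worded identically in both arms, on injuries or symptoms linked to changes in physical activity or diet since the last survey. A question on any new health problem would be too broad, because the plan ties each adverse event to a DSMB report within 48 hours.
2. Tabulate these solicited events by arm for the DSMB, with volunteered events in a separate table.
3. State that solicited non-serious events reach the DSMB in periodic summary tables, so that they do not each trigger an individual report.
4. Reconcile Adverse Event Monitoring with section 2b on which events coaches report.

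The cost is about a minute on two existing calls, a higher reported event count and some added reporting work, which step 3 limits. Men already past a survey will not have been asked, so the tables should state from when the question was in use.
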